Protocol Letter of Amendment

SARS-CoV-2 Vaccination Strategies in Previously Hospitalized and Recovered COVID-19 Patients

3 August 2021

NCT04969250

International Network for Strategic Initiatives in Global HIV Trials
Leadership Group
University of Minnesota
[name]
[name]

Letter of Amendment #1

Date: 03 August 2021

To: Site Investigators and Study Staff

Institutional Review Boards/Ethics Committees

From: INSIGHT 016 Study Team ([name], Protocol Chair)

Protocol: INSIGHT 016 Protocol (VATICO)

Version 1.0, 07 June 2021

Vaccination for Recovered Inpatients with COVID-19 (VATICO)

Subject: Letter of Amendment to (1) Clarify Visit Schedule and (2) Correct Informed Consent

The following information impacts the INSIGHT 016 (VATICO) study and must be forwarded to all responsible Institutional Review Boards (IRBs) and Ethics Committees (ECs) as soon as possible for their information and review. This Letter of Amendment (LOA) must be approved by all responsible IRBs/ECs, as well as any other entities as applicable to each site, and per the policies and procedures of each site.

Information to be Clarified:

(1) Protocol:

In Section 9.1 (Screening/Baseline and Follow-up Assessments), the description of Figure 2 includes the text, "Every 4 weeks from baseline through Week 24, all participants will be contacted either for a face-to-face visit (indicated in figure) or by phone." It then refers the reader to Appendix B (Schedule of Assessments), but the contacts are not listed. These 4-weekly contacts are referenced in the sample informed consent (Appendix A), and are the intent of the protocol.

As shown in Figure 2, in-person visits are required for all participants at Weeks 12, 24, and 48. Additional in-person visits are required for vaccination at Week 4 or Week 16, for those randomized to receive two doses of vaccine. Otherwise, 4-weekly contacts will be by phone or other electronic means at Weeks 4 (all except group I2, being seen in person for vaccination), 8, 16 (all except group D2, being seen in person for vaccination), and 20. There is no structured data collection or study procedures to be conducted at these contacts; they are intended to maintain contact with the participant and guide them through the protocol.

(2) Informed Consent Form:

Under WHAT DO I HAVE TO DO IF I AM IN THIS STUDY?" (page 41 in the main protocol document) the last sentence of the first paragraph states, "If you have already been

[contact] • [contact] • www.insight-trials.org

vaccinated, you cannot be in this study." This is incorrect. Per exclusion criterion 1 (Section 7.2), individuals who were vaccinated before randomization into TICO are eligible to participate in VATICO.

Amendment

(1) Protocol:

In Section 9.1.2 (Follow-up Assessments) the following is added as paragraph 4: Participants will be contacted every 4 weeks through Week 24. At 4-weekly timepoints where there is not already participant contact for vaccination or data collection, this will occur by phone or other electronic medium. These contacts are intended to keep participants engaged and assist them in following their randomized vaccination schedule.

Footnote 7 is added to the table in Appendix B (Overview of Study Procedures):

7. All participants will have study contact every 4 weeks. This will occur by phone or other electronic medium if there are no other study requirements at that timepoint.

(2) Informed Consent Form:

The Sample Informed Consent (Appendix A) has been amended as follows Under WHAT DO I HAVE TO DO IF I AM IN THIS STUDY?" (page 41 in the main protocol document) the last sentence of the first paragraph now reads, "If you got vaccinated after you joined the TICO study, you cannot be in this study." Version 1.1 of the Sample Informed Consent, dated 03 August 2021, accompanies this LOA.

Implementation:

- This amendment will be incorporated into the next formal protocol revision (version 2.0).
- This LOA and revised consent should be submitted to the IRBs/ECs per institutional policy and approved prior to implementation.
- A copy of this LOA should be filed in the site study binders along with the current protocol.

**NCT04969250**

## Analysis of Baseline Characteristics

Baseline characteristics of the four randomized groups in the 2x2 factorial trial will be summarized with summary statistics, including means (standard deviations), medians (25th, 75th percentiles), and percentages. Descriptive summaries of baseline characteristics will be carried out separately for those assigned an investigational agent in TICO and those assigned a placebo. Characteristics summarized will include baseline factors collected prior to randomization in TICO as well as follow-up data collected in TICO prior to randomization to the 2x2 factorial in VATICO.

## Analysis of the Primary Efficacy Endpoint

Analysis will be intention to treat and include all participants including those assigned an investigational agent in TICO and those assigned a placebo in TICO. Quanterix antibody levels at VATICO baseline and at Weeks 12, 24, and 48 will be summarized with box plots by immediate/ deferred, by one/two doses, and by each arm in the 2x2 factorial.

For the comparison of Quanterix antibody levels at Week 48 (the primary endpoint), levels will be log10 transformed and evaluated with analysis of covariance that includes indicators for each factor of the factorial. An interaction test will be carried out between the two factors as well. The antibody level prior to randomization into VATICO, vaccination prior to enrolling in TICO, and assignment to an investigational agent in TICO will be included as covariates to reduce the residual standard error and improve efficiency of the primary comparisons.

Table 1. Power to detect various geometric mean ratios with n = 66 VATICO participants assuming residual standard error of 0.6787 estimated from AZ and MP TICO participants Quanterix antibody levels at baseline and 28 weeks.

	Geometric Mean Ratio					
	1.2	1.5	2.0	3.0	4.0	6.0
Power	7%	18%	43%	80%	94%	>99%

The log10 transformation will be undertaken as is conventional for NAb measurements (as the distribution of log responses is generally closer to a normal distribution), and then the estimates and confidence intervals will be anti-logged to provide estimates and confidence intervals for the ratio of GMRs. A GMR of one indicates that there is no difference between treatment groups in NAb response, for example, among participants who were randomized to immediate compared with those randomized to deferred vaccination. A GMR less than 1.0 provides indication of lower NAb response among those who received immediate compared to those who received vaccination deferred.

The percentage of participants with a 4-fold increase in antibody levels from baseline will be summarized for each factor in the 2x2 factorial using Mantel-Haenszel chi-square statistics.

These analyses will be repeated for participants randomized to an investigational agent in TICO and to a placebo in TICO. These analyses will also be repeated for the Quanterix antibody levels at Week 12 as well as at Week 24.

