## **Analyses of Other Endpoints and Subgroups**

Descriptive summaries will be reported for the composite safety outcome of grade 3 or 4 AE, SAE, or death for the one versus two dose strategy. Similar summaries will be reported for the one vs two dose strategies as well as for the immediate vs deferred strategies for the composite endpoint of SAE or death through Week 24. Non-adherence to the assigned vaccination schedule will be summarized similarly as well.

A number of additional subgroup analyses are planned for each treatment comparison, taking advantage of the data collected at baseline and during follow-up on TICO. Subgroup analyses for each primary objective and the comparisons of TICO active and placebo groups will be performed using regression analysis. In addition to subgroups according to the other factor in the factorial design and the randomization assignment in TICO, prior vaccination at entry to TICO, subgroups according to age, gender, race/ethnicity, geographic region, duration of infection at time of randomization, severity of infection as measured by the highest ordinal category experienced and time to sustained recovery, baseline antigen and antibody level in TICO, and baseline antibody level at the time of randomization to VATICO will be carried out. These analyses will be performed by including an interaction term with treatment in the regression model with the antibody level prior to randomization into VATICO included as a covariate.

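### Does reading the immediate/deferred GMR as antibody response mislead, given that the arms are at different times since vaccination at each visit?

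*SAP*

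**What the plan says.** The SAP section Analysis of the Primary Efficacy Endpoint sets an intention-to-treat analysis of covariance of log10 Quanterix level at Week 48, with an indicator for each factor. Covariates are the VATICO baseline level, vaccination before TICO and TICO assignment. It justifies the log scale by saying that "the distribution of log responses is generally closer to a normal distribution". It then interprets the result: "A GMR of one indicates that there is no difference between treatment groups in NAb response", with the example "among participants who were randomized to immediate compared with those randomized to deferred vaccination". The next sentence is "A GMR less than 1.0 provides indication of lower NAb response among those who received immediate compared to those who received vaccination deferred". The section ends: "These analyses will also be repeated for the Quanterix antibody levels at Week 12 as well as at Week 24". It also plans box plots of the levels at baseline and Weeks 12, 24 and 48, including one set for each of the four arms.

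The section Analyses of Other Endpoints and Subgroups adds: "Non-adherence to the assigned vaccination schedule will be summarized similarly as well".

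On timing, the protocol's Letter of Amendment #1 (Information to be Clarified, item 1) states: "Additional in-person visits are required for vaccination at Week 4 or Week 16, for those randomized to receive two doses of vaccine". It assigns Week 4 to group I2 ("Otherwise, 4-weekly contacts will be by phone or other electronic means at Weeks 4 (all except group I2, being seen in person for vaccination") and Week 16 to group D2. All participants are seen in person at Weeks 12, 24 and 48.

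**The concern.** The visits are fixed from randomization, while vaccination is staggered by design. A between-arm ratio at a fixed visit therefore combines how strongly participants responded with how long ago they were vaccinated. At Week 12 it also includes vaccine that D2 has not yet been given.

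If response is taken to mean the strength of the reaction to vaccine, the SAP's rule could produce opposite findings from one underlying truth. Immediate vaccination would look better at Week 12, because the deferred arms are not fully vaccinated. It would look worse at Week 24, because the immediate arms have had longer to wane. The SAP gives no separate interpretation for the two repeats.

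The two interpretive sentences also differ on population. The first speaks of those randomized to each strategy and the second of those who received it. The trial expects some non-adherence, so these groups need not coincide.

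**Working it through.** **1. Table 1 reproduces.** Inputs from the SAP are n = 66 and residual standard error 0.6787 on the log10 scale. Assumed are a 33 v 33 split, a two-sided 5% test, and 60 df (66 less an intercept, two factors and three covariates).

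SE = 0.6787 × √(4/66) = 0.1671. Noncentral t power at log10(GMR)/SE:

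| GMR | 1.2 | 1.5 | 2 | 3 | 4 | 6 |
|---|---|---|---|---|---|---|
| Table 1 | 7% | 18% | 43% | 80% | 94% | >99% |
| Recomputed | 7.5% | 17.9% | 42.6% | 80.2% | 94.4% | 99.6% |

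The normal approximation gives 6.9% at GMR 1.2. The power basis is sound, and the concern does not touch it.

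**2. Time since the additional vaccination visit** (visit week minus 4 for I2, minus 16 for D2):

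| Visit | I2 | D2 |
|---|---|---|
| Week 12 | +8 | −4 |
| Week 24 | +20 | +8 |
| Week 48 | +44 | +32 |

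The 12-week gap is therefore real at every visit. That these visits are second doses is an inference from their being additional visits for the two-dose groups. First-dose weeks are not in the supplied text. Baseline and Week 12 are plausible and are assumed below.

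**3. What timing alone could do.** The documents give no waning rate, so every rate here is an assumption. Suppose peaks are equal and the level falls as (weeks since vaccination)^−k. Time the two-dose arms from the second dose and the one-dose arms from the first dose, because one-dose arms have no second dose. With equal weights, the Week 24 factor GMR is the geometric mean of (20/8)^−k and (24/12)^−k. For k = 1 this is √(0.400 × 0.500) = 0.447.

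| k | Two-dose GMR | One-dose GMR | Factor GMR, Week 24 | Chance of p < 0.05 |
|---|---|---|---|---|
| 0.5 | 0.632 | 0.707 | 0.67 | 18% |
| 1 | 0.400 | 0.500 | 0.45 | 54% |
| 1.5 | 0.253 | 0.354 | 0.30 | 87% |

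At Week 48 the ratios are (44/32)^−k and (48/36)^−k. For k = 1 they are 0.727 and 0.750, so the factor GMR is √(0.727 × 0.750) = 0.74, with a 12% chance of p < 0.05.

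Now suppose instead that vaccination adds the same amount B on the log scale and levels fall by r per week both before and after it. At Week 24 the immediate arm is at L0 + B − 24r and the deferred arm at L0 − 12r + B − 12r. The difference is zero and the GMR is exactly 1.00. The same holds at Week 48. The assumed patterns thus run from no timing effect to a large one.

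**4. What response means in this section.** The box plots, the Week 48 model and the Week 12 and 24 repeats are all stated for antibody levels. The phrase about log responses uses the word for the measured values themselves. On that reading, a GMR below 1 says that levels at that visit are lower under the immediate strategy, which is what the model estimates. A value above 1 at Week 12 and below 1 at Week 24 would be two correct descriptions, not a contradiction.

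**5. Population.** The same section opens by stating intention to treat. That governs the analysis, so the later reference to those who received a strategy is loose phrasing.

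**6. Would an aligned comparison help?** Immediate arms at Week 12 could be set against deferred arms at Week 24. Both two-dose arms are then 8 weeks past their additional visit. In the equal-fold-rise case, where the planned GMRs are exactly 1.00, this contrast equals 2^(84/h) for half-life h in days. That is 1.08 at 728 days and 2.64 at 60 days, because the deferred arms decline for 12 more weeks before vaccination. Its 95% interval would be the estimate times or divided by 10^(2.0003 × 0.1671) = 2.16.

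**The case for a change.** The best case for acting is that rewording costs almost nothing and two parts of the problem need no waning assumption: D2 is short of its Week 16 visit when sampled at Week 12, and the SAP moves from randomized to received. Nothing in the supplied text warns the reader that the fixed-visit ratio includes time since vaccination, and the repeats extend to the 4-fold-increase percentages. If response can mean level, that is a reason to say so.

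The facts stand. The timing difference is real, the phrasing is loose, and a careless report could present a Week 24 result as a weaker response to early vaccination. What does not stand is the step to a change in the plan. The analyses are specified on levels and by randomized group, so an analyst would run the same models with or without different wording. The per-arm box plots over all visits would show the staggered pattern. The aligned model would exchange one mixture for another, and for the one-dose arms its alignment rests on first-dose timing that the supplied text does not give.

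**Conclusion.** No change to the plan is needed. The Week 12, 24 and 48 GMRs are each valid intention-to-treat comparisons of antibody level under two vaccination strategies at a fixed time from randomization. The 12-week difference in time since vaccination is part of what separates those strategies. It affects how the results are described, most of all at Weeks 12 and 24, and leaves the estimator, the test and the power in Table 1 untouched.

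The size of the timing effect is not established. Under the assumed patterns the Week 24 factor GMR from timing alone lies between 0.30 and 1.00, and the documents cannot narrow that range. The conclusion rests on taking response to mean the measured level, which the section's own usage supports, and on the stated intention-to-treat principle governing the population. The timing figures rest on the Week 4 and Week 16 visits being second doses. Part of the protocol was not available, so a fuller definition there cannot be ruled out; it would only strengthen this reading.

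Analysts can settle the matter when reporting: call the GMR a ratio of levels at that visit among those randomized to each strategy, and mention the timing difference beside the Week 12 and 24 results.

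### The Week 12 one-versus-two-dose analysis pools I2 v I1 with D2 v D1, although D2's second-dose visit is not until Week 16

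*SAP*

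**What the plan says.** The SAP section Analysis of the Primary Efficacy Endpoint says that log10 antibody levels at Week 48 will be "evaluated with analysis of covariance that includes indicators for each factor of the factorial". It adds "An interaction test will be carried out between the two factors as well". The 4-fold rise from baseline is to be "summarized for each factor in the 2x2 factorial using Mantel-Haenszel chi-square statistics". The section ends with "These analyses will also be repeated for the Quanterix antibody levels at Week 12 as well as at Week 24" and states no change for Week 12.

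The vaccination schedule is in the protocol's Letter of Amendment #1, under Information to be Clarified, item (1): "Additional in-person visits are required for vaccination at Week 4 or Week 16, for those randomized to receive two doses of vaccine". The same paragraph lists the telephone contacts and excepts group I2 at Week 4. For the later contact it reads "16 (all except group D2, being seen in person for vaccination". All groups attend in person at Weeks 12, 24 and 48.

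Two other SAP outputs bear on the point. Box plots are planned by factor and by each of the four arms. The section Analyses of Other Endpoints and Subgroups plans subgroups by the other factor ("In addition to subgroups according to the other factor in the factorial design and the randomization assignment in TICO"), using an interaction term in the regression model.

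**The concern.** A factorial main effect for dose is informative when the dose contrast exists at both levels of timing. At the Week 12 sample it exists only in the immediate groups. I2 is 8 weeks past its second-dose visit, while D2 is 4 weeks short of its own. D1 and D2 share whatever deferred first dose has been given by then, so the point does not depend on when that dose falls.

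Two misreadings follow. A dose ratio pulled towards 1 could be taken to mean that a second dose adds little. A significant interaction could be taken to mean that timing changes the effect of a second dose, when one of the two groups has not reached that dose. Week 12 is one of only three post-baseline antibody time points, so its results are likely to be read closely.

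**Working it through.** **Inputs.** From SAP Table 1: n = 66 and residual SD 0.6787 on the log10 scale. From the Letter of Amendment: second-dose visits at Week 4 (I2) and Week 16 (D2). Assumed: two-sided 5%; 1:1 dose allocation within each timing group; immediate share p of 0.5, varied from 0.4 to 0.6; the Table 1 SD holding at Week 12, varied from 0.5 to 0.8. The SD was estimated from TICO data at baseline and 28 weeks.

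**Table 1 reproduced.** For a factor main effect, SE = 0.6787 × √(4/66) = 0.167. Noncentral-t power with 64 df at ratios 2, 3 and 4 is 43%, 80% and 94%, matching the table. A one-sided test does not match (89% at ratio 3), which supports the two-sided 5% assumption.

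**What the Week 12 dose coefficient estimates.** Let δ = log10(I2:I1 ratio), with D2 − D1 = 0 by schedule. In the main-effects model each timing group's dose contrast is weighted by its share of participants:

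- pooled effect = p × δ + (1 − p) × 0 = pδ, so pooled ratio = (I2:I1 ratio)^p
- interaction = δ − 0 = δ

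For a ratio of 3 and p = 0.5, the pooled ratio is √3 = 1.73.

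**Power at Week 12, I2:I1 ratio 3.** The pooled analysis has effect p × 0.477 and SE 0.167. Its df is 60 (66 less intercept, two factors and three covariates). The I2 v I1 contrast has effect 0.477 and SE = 0.6787 × √(4/(66p)), which is 0.236 at p = 0.5. Its df is 59 in the four-cell model, or 66p − 5 using the immediate arms only. The ranges below span these two df choices.

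| Immediate share | SD | Pooled target ratio | Pooled power | I2 v I1 power |
|---|---|---|---|---|
| 40% | 0.6787 | 1.55 | 20% | 41–43% |
| 50% | 0.6787 | 1.73 | 29% | 50–51% |
| 60% | 0.6787 | 1.93 | 39% | 57–59% |
| 50% | 0.5 | 1.73 | 48% | 75–77% |
| 50% | 0.8 | 1.73 | 22% | 38–39% |

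**I2:I1 ratio needed for 80% power (SD 0.6787).**

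| Immediate share | Pooled | I2 v I1 |
|---|---|---|
| 40% | 15.5 | 5.7–6.0 |
| 50% | 8.9 | 4.7–4.9 |
| 60% | 6.2 | 4.1–4.2 |

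**Simulation.** There were 20,000 runs with cells of 17, 17, 16 and 16 and the effect in the immediate arms only. With no effect, the pooled test rejected in 5.2% of runs and the interaction test in 5.0%, so type I error is preserved. With a ratio of 3, the pooled ratio was 1.76 with power 29%. The immediate share there is slightly above one half: 3^(34/66) = 1.76. The interaction ratio was 3.00, rejected in 29% of runs. The I2 v I1 ratio was 3.00, with power 52%.

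**4-fold rise (illustrative rates, all assumed).** Take I1 40%, I2 80% and D1 = D2 = 10%. The risk difference is 40 points in the immediate arms and (40 + 0)/2 = 20 points pooled. With Mantel-Haenszel strata defined by timing, which the SAP does not specify, power is 55% pooled v 70% for I2 v I1. Deferred rates of 5% to 20% move the pooled figure from 61% to 46%.

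**The case against.** The strongest reply is that nothing here is invalid. Under intention to treat, the pooled Week 12 comparison is a randomized contrast of assigned strategies with correct type I error. The SAP claims no Week 12 power and does not call the coefficient a second-dose effect. The model with the interaction term also contains I2 v I1, and box plots by arm and subgroups by the other factor are planned. All of that is true. It limits the point to a secondary analysis and shows that the remedy needs no new model.

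It does not remove the point. Box plots give no estimate or interval. The subgroup section does not mention Week 12 and relies on the same interaction term. The Week 12 estimate the SAP does specify is the diluted one, and nothing warns the reader.

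Two further cautions stand. The protocol text available is the Letter of Amendment and part of the SAP is missing, so a qualification elsewhere cannot be ruled out; none appears in the analysis section, where it would belong. The 4-fold-rise figures rest on invented rates and assumed strata, and only illustrate the direction.

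**Conclusion.** The concern holds for the Week 12 repeat. As written, the dose analysis there estimates the I2 v I1 log effect shrunk by about the immediate share, and the interaction test cannot address effect modification by timing. The shrinkage follows from the schedule, adherence aside. Its size depends on the immediate share, which the available text does not state. The loss of power depends also on the SD and the true ratio, but I2 v I1 was the more powerful comparison in every scenario examined although it rests on only part of the participants. The power figures compare two analyses of the same data and do not contradict any claim in the SAP. The Week 48 primary analysis is not affected, so this should be fixed but does not threaten the main result.

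**What to change.** In the SAP's Analysis of the Primary Efficacy Endpoint, replace the unmodified repeat with a Week 12 rule:

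- Estimate one v two doses at Week 12 as I2 v I1, by an ANCOVA contrast with the same covariates.
- Apply the same restriction to the Week 12 4-fold-rise comparison by dose.
- Omit the dose-by-timing interaction test at Week 12.
- If the pooled dose ratio is also shown, label it a contrast of assigned strategies taken before D2's scheduled second dose.

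The factorial model can stay at Week 24, with a note that I2 is 24 − 4 = 20 weeks and D2 is 24 − 16 = 8 weeks past the second-dose visit, so the interaction includes time since dose. The same caveat applies in kind at Week 48 (44 v 32 weeks).

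Optionally, add a dose contrast aligned at 8 weeks after the second-dose visit: I2 v I1 at Week 12 with D2 v D1 at Week 24. The deferred first-dose time should first be confirmed in the full protocol.

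The cost is a few sentences and one model contrast, with no new samples, visits or participants.
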